1.0 INTRODUCTION

This document is a clinical investigation plan (CIP) for the WAVE-MAP AF clinical investigation. This clinical investigation is intended to characterize the left atrial substrate using the Advisor™ HD Grid Mapping Catheter, Sensor Enabled™ in an HD Wave configuration and correlate different factors with 12-month success after a single ablation procedure using a pulmonary vein isolation (PVI) approach without further substrate modification. This clinical investigation will be conducted as a post-market study and is intended to support marketing claims for the Advisor™ HD Grid Mapping Catheter, Sensor Enabled™ (GRID).

[REDACTED] This clinical investigation is sponsored by Abbott.

This clinical investigation will be conducted in accordance with this CIP. All investigators involved in the conduct of the clinical investigation will be qualified by education, training, or experience to perform their tasks and this training will be documented appropriately.

1.1 **Background and Rationale**

1.1.1 **Background**

It has been estimated that 20.9 million men and 12.6 million women have Atrial Fibrillation (AF) worldwide.¹² AF has a prevalence of approximately 3% in adults aged 20 years or older.^{3,4} Additionally, one in four middle-aged adults in the US and Europe will develop AF in their lifetime.^{5,6} In Australia, 5% of people aged 55 years or older have AF, and this number is projected to rise to 6% by 2034⁷. These estimates suggest that AF is a condition that impacts a significant number of people with implications for their healthcare systems.

AF remains a major cause of stroke, heart failure, sudden death, and cardiovascular morbidity. In a meta-analysis of contemporary, well-controlled, randomized clinical trials in AF, the average annual stroke rate is 1.5% with an annualized death rate of 3% in anticoagulated AF patients.⁸ A minority of these deaths are related to stroke, while sudden cardiac death and death from progressive heart failure are more frequent, emphasizing the need for interventions beyond anticoagulation.^{9,10} AF is also associated with high rates of hospitalization, commonly for AF management, but often hospitalization is also due to heart failure, myocardial infarction, and treatment associated complications.^{11,12,13} Additionally, patients with AF have significantly poorer quality of life than healthy controls, experiencing a variety of symptoms including lethargy, palpitations, dyspnea, chest pain, sleeping difficulties, and mental distress.^{14,15,16,17}

AF is generally divided into three different types based on the frequency of the AF: paroxysmal, persistent, and long-standing persistent. Paroxysmal AF (PAF) is defined as AF that terminates spontaneously or with intervention within 7 days of onset. Persistent AF (PsAF) is defined as continuous AF that is sustained beyond 7 days. Long-standing persistent AF (LSAF) is defined as continuous AF of greater than 12 months duration.

Per Calkins, et al in the 2017 HRS/EHRA/ECAS/APHRS/SOLAECE Expert Consensus Statement on Catheter and Surgical Ablation of Atrial Fibrillation (2017 Consensus)¹⁸, catheter ablation is a treatment option for all three types. Pulmonary vein isolation (PVI) is a recommended approach by the consensus paper for all de novo AF ablation procedures. PVI alone does not cure all AF, and other techniques have been studied to supplement PVI ablation and improve outcomes. Substrate modification beyond

Clinical Investigation Plan

isolation of the pulmonary veins is one type of supplementary ablation. Outcomes of substrate modification, when added to PVI, have shown mixed results. Further characterization of the atrial substrate is needed to identify ablation targets to improve outcomes. Several studies have shown some benefit identifying low-voltage zones (LVZs) and ablating those targets in addition to PVI for persistent atrial fibrillation. Not all subjects have LVZs though, and mapping is critical to identify which subjects will respond to PVI only, and which require further substrate modification. It is hypothesized that it is more advantageous to characterize subjects by the amount of LVZ substrate in the left atria, rather than into PAF, PsAF, or LSAF, for the purposes of identifying the optimal treatment approach.

There are two traditional means of identifying LVZs: delayed enhancement magnetic resonance imaging (DEMRI) and traditional mapping catheters. DEMRI must be performed outside of the EP lab. The usefulness of DEMRI for detecting fibrosis requires extensive MRI experience and is dependent on image contrast and continuity parameters. When collecting points using traditional mapping catheters, only a single bi-pole is considered for any give acquisition. This makes voltage measurements susceptible to inaccuracies resulting from misalignment of the bi-pole with the propagating wave-front.

GRID was introduced to the European market in 2017. The GRID, with equispaced multipolar grid electrodes, provides known bi-pole spacing in orthogonal directions. GRID can discriminate voltage differences in two directions which provides enhanced directionality and amplitude detection. This is done by using an HD Wave electrode configuration with AutoMap (with best duplicate enabled) during electro anatomical map creation (see Appendix IX). It is hypothesized that electro anatomical mapping using the GRID with HD Wave will provide high-density and high-resolution mapping for improved insight to the extent of structural disease.

In this study, the aim is to use the GRID to characterize the atrial substrate and develop a model for predicting recurrence rates after a single procedure using a PVI only approach and a contact catheter.

1.1.2 Rationale for Conducting this Clinical Investigation

This study will provide insight into how substrate characteristics, as measured by GRID, can identify subjects who will not benefit from additional substrate modification beyond PVI. This may result in future recommendations for treatment based on HD Wave mapping of baseline substrate so that additional, unnecessary ablations along with their potential risks can be avoided. There have been no studies to date correlating substrate characteristics, as measured using HD Wave mapping, to outcomes.

[figure not shown]
2.0 CLINICAL INVESTIGATION OVERVIEW

2.1 Clinical Investigation Objectives

The primary objective of this study is to characterize low-voltage substrate, as identified via HD Wave mapping in sinus rhythm, and identify associations with 12-month recurrence rates after a single pulmonary vein isolation (PVI) with a contact force RF ablation catheter.

Other objectives of this study include:

- Analyze additional maps and data collected with GRID and associations with 12-month recurrence rates, such as:

Clinical Investigation Plan

- Voltage maps using different configurations recreated post procedure¹
- Voltage maps using different thresholds for low-voltage
- Fractionation maps

● [REDACTED]

2.2 Device(s) To Be Used in the Clinical Investigation

2.2.1 Name of the Device(s) Under Investigation

All devices used in this clinical study must have proper regulatory approval and will be used according to their indications for use and Instructions for Use (IFU).

The devices that will be used in this clinical study are summarized in Table 1.

Table 1. Clinical Study Devices

Device name	Model/Type	Manufacturer
Advisor™ HD Grid Mapping Catheter, Sensor Enabled™	D-AVHD-DF16	SJM
EnSite Precision™ Cardiac Mapping System v 2.2 or later	H702496	SJM
Advisor™ HD Grid Mapping Catheter, Sensor Enabled™ Software Kit (License entitlement to use GRID with EnSite Precision 2.2)	H702519	SJM
Sensor Enabled™ Diagnostic Catheter Cable	D-AVSE-CBL22	SJM
EnSite Precision™ Surface Electrode Kit	EN0020-P	SJM
EnSite™ AutoMap Module	H702498	SJM
EnSite™ AutoMark Module	H702499	SJM
EnSite™ Contact Force Module	H702500	SJM
TactiCath™ Contact Force Ablation Catheter, Sensor Enabled™	A-TCSE-D A-TCSE-F A-TCSE-J	SJM

¹ For example, after receiving the EnSite case archive from the site, the Sponsor would recreate what the voltage map would have looked like using a Standard configuration as opposed to the HD Wave configuration to compare differences.

[REDACTED]

Clinical Investigation Plan

	A-TCSE-DD A-TCSE-FF A-TCSE-JJ A-TCSE-DF A-TCSE-FJ	
TactiSys™ Quartz Equipment	PN-004 400	SJM
Cool Point™ Pump v24 or greater	85784 (OUS)	SJM
Ampere™ RF Generator v1.04 or greater	H700489 (OUS)	SJM

Additional commercially available tools may be used in this clinical study per physician's discretion and per device IFUs unless specifically prohibited in this CIP.

2.2.2 Indication for Use

The Advisor™ HD Grid Mapping Catheter, Sensor Enabled™, is indicated for multiple electrode electrophysiological mapping of cardiac structures in the heart, i.e., recording or stimulation only. This catheter is intended to obtain electrograms in the atrial and ventricular regions of the heart.

All devices will be used according to their approved labelling in this study.

Please refer to the IFUs for additional information regarding the devices used in this clinical investigation.

3.0 CLINICAL INVESTIGATION DESIGN

This is a post-market, single-arm, multi-center, prospective interventional study of the Advisor™ HD Grid Mapping Catheter, Sensor Enabled™. This study is aimed at determining correlations between pre-ablation mapping characteristics and outcomes after catheter ablation of atrial fibrillation. [REDACTED]

Endpoints will be analyzed when all subjects have completed their 12-month follow up visits.

3.1 Clinical Investigation Procedures and Follow-up Schedule

Subjects will be followed until they complete their 12-month visit. Clinical Investigation visits will occur at Baseline (confirmation of eligibility), Index Procedure, 3 months, 6 months, and 12 months. The flow chart below summarizes the visits and study procedures.

[REDACTED]

Clinical Investigation Plan

[figure not shown]

Figure 1 Clinical Investigation Flow Chart

3.2 Measures Taken to Avoid and Minimize Bias

Measures taken to avoid or minimize bias include the following:

- All analyses of mapping data will be centralized and performed using proprietary software by an independent reviewer.

Clinical Investigation Plan

- To minimize selection bias, investigators are required to screen consecutive patients with planned de novo AF ablation procedures and record them on a screening log.
- Strict inclusion/exclusion criteria are included in this CIP.
- A standardized mapping and ablation protocol has been defined.
- Individuals taking measurements from EnSite maps will not have access to the outcome data of the associated subject.

3.3 Suspension or Early Termination of the Clinical Investigation

While no formal statistical rule for early termination of the clinical investigation for insufficient effectiveness of the device under investigation is defined, the Sponsor reserves the right to discontinue the clinical investigation at any stage or reduce the follow-up period with suitable written notice to the investigator. Possible reason(s) may include, but are not limited to:

- A new unreasonable risk to the participating subjects has been identified such as an unanticipated increase in complaint rates related to the study.
- Further product development is cancelled.

Should the clinical investigation be discontinued by the Sponsor, subjects will be followed per routine hospital practice with device-related AEs reported to the Sponsor as per vigilance/commercial reporting requirements. The investigator shall return all clinical investigation materials to the Sponsor and provide a written statement to the EC (if applicable). All applicable clinical investigation documents shall be subject to the same retention policy as detailed in Section 11.0.

A Principal Investigator, EC or regulatory authority may suspend or prematurely terminate participation in the clinical investigation at the investigational site(s) for which they are responsible. The investigators will follow the requirements specified in the Clinical Trial Agreement.

If the Sponsor suspends or prematurely terminates the clinical investigation at an individual site in the interest of safety, the Sponsor will inform all other Principal Investigators.

If suspension or premature termination occurs, the Principal Investigator or authorized designee will promptly inform the enrolled subjects at his/her site, if appropriate, and return patients to their standard medical treatment.

4.0 ENDPOINTS

4.1 Primary Endpoint and Rationale

The primary outcome is one-year success, defined as freedom from AF/AFL/AT after removal from antiarrhythmic drug therapy as assessed from the end of the 3-month blanking period to 12 months following a single ablation procedure.

Occurrence of isthmus-dependent atrial flutter, if confirmed during electrophysiology testing, should not be considered a failure for this outcome.

This endpoint is based on the recommendations from the 2017 HRS consensus paper.¹⁸

Clinical Investigation Plan

4.2 Additional Data

Additional data to be collected will include the following:

- Acute procedural success, defined as electrical isolation of all pulmonary veins.
- Success post blanking period through 12 months using different definitions, including:
 - Freedom from symptomatic AF/AFL/AT after removal from AAD therapy
 - Single procedure clinical success defined as freedom from symptomatic AF/AFL/AT without a new or increased dose of class I or III AAD
- Data from EnSite maps using both HD Wave and Standard mapping modes² in both sinus rhythm and AF including but not limited to:
 - Left atrial area using different boundaries (e.g. with and without LAA, etc.)
 - Low voltage area and proportion of left atria with low voltage using different cutoffs for voltage
- Rates of recurrence not due to PVI gap for subjects with repeat electrophysiology studies
- LA volume and diameter
- Adverse events including any device-, procedure-, or death-related events
- Other baseline characteristics including but not limited to:
 - Time with AF
 - Type of AF
 - Sex
 - BMI
 - General medical history
 - Cardiovascular history
 - Arrhythmia history
 - NYHA classification
 - LVEF
 - Presence of pacemaker
- Procedural characteristics, including but not limited to:
 - Power, temperature, and contact force
 - Procedure time
 - Mapping time
 - Cardioversions (if applicable)

² Difference in each measurement between the different mapping modes will be compared.

Clinical Investigation Plan

- Anesthesia
- Fluoroscopy time

5.0 SUBJECT SELECTION AND WITHDRAWAL

5.1 Subject Population

This clinical investigation will enroll male and female subjects from the general atrial fibrillation population. Subjects must meet all eligibility criteria and provide written informed consent prior to conducting any investigation-specific procedures not considered standard of care.

5.2 Subject Screening and Informed Consent

5.2.1 Subject Screening

Subjects must be screened for clinical investigation eligibility by a member of the site's clinical investigation team previously trained to the CIP and delegated to do so. All screened patients will be entered on a site-specific screening log.

In case the patient does not meet all inclusion criteria or meets any of the exclusion criteria, the patient is considered a screening failure. The Principal Investigator or the delegated clinical investigation personnel will record the reason for the screen failure on the screening log.

To minimize bias throughout the enrollment period for this study, consecutive de novo AF patients with planned ablation must be screened³, offered the study if they meet criteria, and added to a screening log.

Potential patients presenting at the clinical sites will be fully informed about the clinical investigation, following the established Informed Consent process (described in Section 5.2.2). Patients meeting all inclusion criteria and no exclusion criteria will be asked to sign an Informed Consent form if they wish to participate in the clinical investigation.

Once a duly dated and signed Informed Consent form is obtained, the clinical investigation-specific procedures may begin.

5.2.2 Informed Consent

The Patient Informed Consent form must receive approval from the Sponsor and EC/IRB prior to beginning clinical investigation enrollment.

The Investigator or his/her authorized designee (if applicable) will conduct the Informed Consent process, as required by applicable regulations and the center's EC. This process will include a verbal discussion with the subject on all aspects of the clinical investigation that are relevant to the subject's decision to participate, such as details of clinical investigation procedures, anticipated benefits, and potential risks of clinical investigation participation. Subjects must be informed about their right to withdraw from the clinical investigation at any time and for any reason without sanction, penalty or loss of

³ This does not necessarily mean that the patient must be approached if their medical records indicate that they would not qualify.

Clinical Investigation Plan

benefits to which the subject is otherwise entitled. Withdrawal from the clinical investigation will not jeopardize their future medical care or relationship with the investigator.

During the discussion, the Principal Investigator or his/her authorized designee will avoid any improper influence on the subject and will respect subject's legal rights. Financial incentives will not be given to the subject. Subjects may be compensated for time and travel directly related to the participation in the clinical investigation. The subject shall be provided with the Informed Consent form written in a language that is understandable to the subject and has been approved by the center's EC. The subject shall have adequate time to review, ask questions, and consider participation. The Principal Investigator or his/her authorized designee will make efforts to ensure that the subject understands the information provided. If the subject agrees to participate, the Informed Consent form must be signed and dated by the subject and thereafter by the person obtaining the consent prior to any clinical investigation-specific procedures. The signed original will be filed in the subject's hospital or research charts, and a copy will be provided to the subject.

Failure to obtain informed consent from a subject prior to clinical investigation enrollment should be reported to Sponsor within 5 working days and to the reviewing center's EC according to the EC's reporting requirements.

If, during the clinical investigation, new information becomes available that can significantly affect a subject's future health and medical care, the Principal Investigator or his/her authorized designee (if applicable) will provide this information to the subject. If relevant, the subject will be asked to confirm their continuing informed consent in writing.

5.2.2.1 Special Circumstances for Informed Consent

Incapacitated individuals, defined as persons who are mentally ill, mentally handicapped, or individuals without legal authority, are excluded from the study population. Individuals under the age of 18 or age of legal consent are excluded from the study population. Individuals unable to read or write are excluded from the study population. Pregnant or breastfeeding women are excluded from the study population.

5.3 Eligibility Criteria

5.3.1 General Eligibility Criteria

Assessment for general eligibility criteria is based on medical records of the site and interviews with candidate patients. If some of the clinical and laboratory tests are not included in site standard tests, they must be done but after written informed consent is obtained. Patients must meet ALL the inclusion criteria to be considered for the clinical investigation. If ANY of the exclusion criteria are met, the patient is excluded from the clinical investigation and cannot be enrolled.

5.3.2 Inclusion Criteria

5.3.2.1 General Inclusion Criteria

1. Documented atrial fibrillation with planned endocardial ablation procedure
2. Age 18 years or older

Clinical Investigation Plan

3. Able and willing to provide written informed consent prior to any clinical investigation related procedure
4. Able and willing to complete all required study procedures through 12 months

5.3.3 Exclusion Criteria

5.3.3.1 General Exclusion Criteria

1. Long-standing persistent atrial fibrillation defined as continuous AF greater than 12 months in duration
2. Previous ablation or surgery in the left atria
3. Implanted left atrial appendage occluder
4. Implanted mitral or tricuspid valve replacement
5. Implanted cardiac defibrillator (ICD)
6. Participation in another clinical investigation that may confound the results of this study
7. Pregnant or nursing
8. Presence of other anatomic or comorbid conditions, or other medical, social, or psychological conditions that, in the investigator's opinion, could limit the subject's ability to participate in the clinical investigation or to comply with follow-up requirements, or impact the scientific soundness of the clinical investigation results.
9. Life expectancy less than 12 months

5.4 Subject Enrollment

A patient is considered enrolled in the clinical investigation from the moment the patient provides written informed consent, has been confirmed to meet all inclusion criteria and none of the exclusion criteria and has had the mapping catheter inserted into the subject's vasculature.

5.5 Subject Withdrawal

Each enrolled subject shall remain in the clinical investigation until completion of the required follow-up period; however, a subject's participation in any clinical investigation is voluntary and the subject has the right to withdraw at any time without penalty or loss of benefit. Conceivable reasons for discontinuation may include, but not be limited to, the following:

- Subject death
- Subject voluntary withdrawal
- Subject lost-to follow-up as described below
- Subject has a thrombus **and** is withdrawn per Section 6.2
- Index ablation procedure is aborted prior to collection of at least one of the required maps.
- Operator is not able to achieve pulmonary vein isolation.
- Subject becomes a screen failure after consent

Clinical Investigation Plan

The Sponsor must be notified of the reason(s) for subject discontinuation. The site will provide this information to the Sponsor. Investigators must also report this to their respective EC as defined by their institution's procedure(s).

No additional follow-up will be required or data recorded from subjects once withdrawn from the clinical investigation.

However, if a subject withdraws from the investigation due to problems related to the safety or performance of the device under investigation, the investigator shall ask for the subject's permission to follow his/her status/condition outside of the clinical investigation.

In case of subject withdrawal of consent, the site should make attempts to schedule the subject for a final clinical investigation visit. At this final follow-up visit, the subject will undergo the assessments required at the 12-month follow up visit.

If subjects are enrolled into the clinical investigation and are later found to have met exclusion criteria or not all inclusion criteria after the ablation procedure, these subjects will continue follow-up in the clinical investigation and may be included in the analysis population. A protocol deviation must be completed on the applicable CRF. Such subjects identified prior to the index procedure should be identified as screen failures and a protocol deviation is not necessary.

Lost-to-Follow-up

If the subject misses two consecutive scheduled follow-up time points and the attempts at contacting the subject detailed below are unsuccessful, then the subject is considered lost-to-follow-up. Site personnel shall make all reasonable efforts to locate and communicate with the subject (and document these efforts in the source documents), including the following, at each contact time point:

- A minimum of two telephone calls on different days over the specified follow-up windows to contact the subject should be recorded in the source documentation, including date, time and initials of site personnel trying to make contact.
- If these attempts are unsuccessful, a letter (certified if applicable) should be sent to the subject.
- If a subject misses one or more non-consecutive follow-up contact time points, it will be considered a missed visit. The subject may then return for subsequent visits. If the subject misses two consecutive time points and the above-mentioned attempts at communicating with the subject are unsuccessful, the subject can be considered lost-to-follow-up.

Note: Telephone contact with General Practitioner, non-clinical investigation cardiologist or relative without the presence of the subject or indirect documentation obtained via discharge letters will not be considered as subject contact.

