6.4 Follow-up Assessments

The following sections describe the follow-up visits and procedures. All windows are stated with respect to the index procedure unless otherwise noted. It is recommended to follow the HRS Consensus guidelines for follow-up screening depending on type of AF (e.g. paroxysmal vs. persistent). A 12-lead

⁸ This may include ablation to address the carina within the WACA circle per the investigator's discretion.

⁹ Site's standard of care is PVI-only, so no other substrate modification should be performed.

¹⁰ For example, "AF resolved to sinus rhythm during ablation of lesion #23".

Clinical Investigation Plan

ECG is recommended any time the subject returns to the clinic from 3- to 12-months post index procedure.

6.4.1 3-Month Follow Up (77 to 105 Days Post Index Procedure)

The blanking period ends on the day of the 3-month follow up visit. It is recommended the subject not be taking any class I or III AAD after the 3-month visit unless there is recurrence of AF. At the 3-month visit, the following procedures will be completed:

- Check for symptoms of recurrence
- Perform 12-lead ECG
- Document Adverse Events and Protocol Deviations
- Document AAD usage
- Document any recurrences including any details of repeat electrophysiology studies
- Instruct the subject to contact the site if they experience any symptoms of recurrence. If there are any symptoms noted after the 3-month visits through the 12-month visit, check for recurrence using 12-lead ECG or other form of monitoring per site's standard practice.

It is also recommended to provide the subject with an event monitor for recording at regular intervals (e.g. monthly) or for symptomatic events through the 12-month visit.

After the 3-month visit through the end of the study, any signs or symptoms of recurrence should be recorded, and the subject should have either a 12-lead ECG or other form of ECG monitoring per the site's standard practice to determine if recurrence has occurred.

6.4.2 6-Month (169 to 197 Days) Follow Up Phone Visit

Within two weeks of the 6-month time point post index procedure, the subject will be contacted via telephone (or seen in-clinic if standard of care) for the following assessments

- Check for symptoms of recurrence
- Document Adverse Events and Protocol Deviations
- Document AAD usage

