- If there are symptoms of recurrence present, the subject should have either a 12-lead ECG or other form of ECG monitoring to determine if recurrence has occurred.
- Document any recurrences including details of any repeat electrophysiology studies

For persistent AF subjects, it is also recommended that a 24-hour holter be performed at the 6-month time point.

6.4.3 12-Month Follow Up Visit (335 to 395 Days Post Index Procedure)

The 12-Month visit will include the following procedures:

- Check for symptoms of recurrence
- Perform 12-lead ECG

Clinical Investigation Plan

- Record Adverse Events and Protocol Deviations. Make sure to record the status of each ongoing event at the time of study exit.
- Document AAD usage
- Complete 24-hour continuous ECG monitoring¹¹, and record results on the applicable CRF
- Document any recurrences including any details of repeat electrophysiology studies

¹¹ This does not have to be done on the day of the visit. It can be done any time during the 12-month visit window.

[REDACTED]

Clinical Investigation Plan

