##### **3.1.3 Survival Analyses**

Survival (SURV) analysis will be conducted to analyze time-to-event variables. Subjects without events will be censored at their last known event-free time point. Subjects withdrawn or otherwise lost-to-follow-up during the follow-up period will be censored at their last known visit. Survival data will be presented using the Kaplan-Meier product limit method. Number of subjects at risk, number of censored subjects, number of events, event free survival rate and standard error of the survival rate at each follow-up time point will be presented in a summary table.

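### The lost-to-follow-up rule lets an unreachable subject be closed out from about Day 197, 138 days before the only post-blanking visit with a required rhythm recording, and no 12-month attempt is stated

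*Protocol*

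**What the plan says.** Protocol 5.5 has two conditions for lost to follow-up, and both must hold: "If the subject misses two consecutive scheduled follow-up time points and the attempts at contacting the subject detailed below are unsuccessful". The attempts are at least two calls on different days and, if those fail, a letter, at each time point. The opening sentence of the rule makes the status automatic once both conditions are met. The last bullet restates the same conditions but makes the status optional. A return to later visits is written only for misses that are not consecutive.

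The same section lists loss to follow-up among the reasons for discontinuation and says: "No additional follow-up will be required or data recorded from subjects once withdrawn from the clinical investigation". A Note adds that "indirect documentation obtained via discharge letters will not be considered as subject contact".

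Protocol 6.4 sets three follow-up contacts: "6.4.1 3-Month Follow Up (77 to 105 Days Post Index Procedure"), then "6.4.2 6-Month (169 to 197 Days) Follow Up Phone Visit", then a 12-month visit at Day 335 to 395. The 12-month visit requires a 12-lead ECG and also "Complete 24-hour continuous ECG monitoring".

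SAP 3.1.3 says: "Subjects withdrawn or otherwise lost-to-follow-up during the follow-up period will be censored at their last known visit". SAP 3.3.1 repeats this for the Kaplan-Meier analysis, rules out imputation, and undertakes to use whatever endpoint data exist in the analysis population.

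**The concern.** With so few contacts, a rule based on two in a row can take effect before the visit that matters most for the primary outcome. Freedom from AF/AFL/AT is assessed from the end of blanking to 12 months, and the only rhythm recording the plan requires in that period is at the 12-month visit. A subject who could not be reached at 3 and 6 months may be reachable at 12, but the protocol does not tell the site to try.

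Section 5.5 is also uneven. When consent is withdrawn, the site should try to arrange a final visit with the 12-month assessments. A subject who has only been out of reach gets no equivalent effort. And because the rule is worded once as automatic and once as optional, two sites could treat identical subjects differently and both be compliant.

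**Working it through.** **Inputs (Protocol 6.4 and Table 2).** 3-month visit, Day 77 to 105. 6-month call, Day 169 to 197. 12-month visit, Day 335 to 395.

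**Step 1: reproduce the windows.** The midpoints are (77 + 105)/2 = 91, (169 + 197)/2 = 183 and (335 + 395)/2 = 365.
- 91 ± 14 gives 77 to 105.
- 183 ± 14 gives 169 to 197, which agrees with the text: "Within two weeks of the 6-month time point post index procedure".
- 365 ± 30 gives 335 to 395.

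The stated windows are internally consistent.

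**Step 2: which pairs can trigger the rule.** Three contacts give two consecutive pairs. The 6- and 12-month pair cannot be complete until the 12-month window has closed, so it forgoes nothing. Only the 3- and 6-month pair can act early.

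**Step 3: timing.** The second miss is complete when the 6-month window closes, at Day 197.
- To the opening of the 12-month window: 335 - 197 = 138 days.
- To nominal 12 months: 365 - 197 = 168 days.
- To the close of the window: 395 - 197 = 198 days.

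Day 197 is the earliest date the windows imply. The rule states no date and gives no response time for the letter, so actual closure may be later.

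**Step 4: effort required before closure.** Two time points × at least two calls = at least four failed calls. Two time points × one letter = two letters. A subject who is reached but does not attend is not lost to follow-up.

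**Step 5: what is forgone.** Blanking runs to the date of the 3-month visit, so the ECG required at that visit is not a post-blanking recording. At 6 months, the 24-hour Holter is a recommendation for persistent AF, and an ECG is otherwise prompted by symptoms. That leaves the 12-month visit as the only post-blanking visit with a required recording. For a subject who missed both earlier contacts, the last scheduled visit attended is the index procedure. Censoring at that visit leaves no post-blanking time in the Kaplan-Meier analysis. A related gap is that the end of blanking has no defined date for someone with no 3-month visit.

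**Step 6: size (assumptions, not document figures).** The sample size section is redacted. Protocol 5.6 gives about 60 subjects as 20% of maximum enrollment, so about 60/0.20 = 300. No loss rate is visible. Suppose 1% to 5% are closed out this way, and 10% to 50% of those could be reached later:
- closed out: 300 × 0.01 = 3 to 300 × 0.05 = 15;
- outcomes recoverable: 3 × 0.10 = 0.3 to 15 × 0.50 = 7.5.

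**The case against.** The strongest reply is that the affected group is narrow, and this stands. Two missed contacts alone do not close anyone out. A reader might take the rule that way, but it also needs failed calls and a letter each time. People who have not answered at least four calls and two letters may well not answer a third round.

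A reader might also infer that a 12-month result from a subject who reappears would be thrown away. The documents do not say so. Section 5.5 opens by keeping enrolled subjects in the study to the end of required follow-up, its closing wording on loss is optional, and SAP 3.3.1 uses available endpoint data. This answers only part of the point: data that nobody is asked to seek, and that 5.5 says are not recorded after withdrawal, will usually not be available.

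A third tempting inference is that the Note bars outside hospital records as evidence of recurrence. It defines only what counts as contact with the subject, and Protocol 6.4 asks sites to document recurrences without limiting them to those treated on site. Nor does SAP 3.1.3 say that censoring overrides a recurrence already documented. What remains is that neither document states which takes precedence.

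Finally, a reader might conclude that the success rate is inflated. That would need loss to be related to recurrence, which the documents do not show. A subject censored before the endpoint window opens is not counted as a success. The population definitions, the logistic regression text and the list of primary analyses are redacted, so how these subjects enter the primary analysis cannot be determined.

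**Conclusion.** The concern holds in a limited form. Section 5.5 permits a subject who misses the 3- and 6-month contacts and cannot be reached at either to be closed out up to 138 days before the 12-month window opens. It states no 12-month attempt and no way back for this pattern, and it words the rule in two ways that need reconciling. Some primary outcomes may be lost as a result.

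The day counts are exact, given the stated windows. The number of outcomes at stake is not known from the documents. The illustration of 0.3 to 7.5 rests wholly on assumed rates and an enrollment of about 300 inferred from the site cap; the true figure is probably small. Neither a bias direction nor an effect on the association between substrate and recurrence is established. The change is worth making because it is cheap and removes an avoidable loss on the primary outcome. The point is not a threat to the study.

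**What to change.** In Protocol 5.5:
- Assign lost-to-follow-up status only when the 12-month window closes (Day 395) without contact.
- Require a 12-month contact attempt for subjects who missed the 3- and 6-month contacts, and let them return for the 12-month assessments.
- Use one wording for the rule, either automatic or optional.
- State that the Note limits only what counts as subject contact, so that recurrences or deaths documented by other providers are recorded as outcome data where consent allows.

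In SAP 3.1.3 and 3.3.1, state that a documented recurrence is an event on its date and is not replaced by censoring at the last visit.

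The cost is a few sentences of amendment, plus one more round of calls and a letter for a few subjects. No visit or procedure is added. Subjects who return only at 12 months will need some antiarrhythmic drug history taken retrospectively, which is less reliable than entries made at 3 and 6 months.
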